#### 4.2.2 CNI/EVR Trough Level Imputation

The exact time-varying trough concentration is not known. Imputation is required to estimate the time-varying concentration from the available trough concentration and dose records. The imputation method is essentially a backward imputation with a forward component (see illustration in [Figure 4-1](#))

[figure not shown]
1. For each patient, the maximum study drug on-treatment date will be created as the analysis cut-off date.
2. Trough concentrations after the analysis cut-off date will be ignored.
3. For patients without the study drug trough concentration at the cut-off date, the last observation will be carried forward to the cut-off date, so all patients will have study drug trough concentrations at the cut-off date (carry-forward imputation).

4. Assuming that a patient had concentration measurements on Days  $x$  and  $y$  ( $x < y$ ), the concentration on Day  $x+1$  to  $y-1$  is assumed to be that of Day  $y$ . The first available trough level will be carried backward to the day of the first dose of respective study drug. Therefore each day from the day of the first dose of respective study drug to the cut-off date will have a trough concentration (carry-backward imputation). The rationale for this imputation is that a concentration measurement may trigger a change in dose, so a measured concentration is more representative of the past than of the future.

**Figure 4-1 Imputation rule for concentration data: 2 hypothetical patients**

(a) Last contact day is after the last dose day + 2 days

- (b) Last contact day is the same day as the last dose day (patient discontinued the study and the study drug on the same day)

#### 4.2.3 LOCF for Laboratory and Vital Sign Data

Summary statistics by visit window for laboratory (including renal) and vital sign variables using two different conventions of the last observation carried forward (LOCF) method.

- LOCF using last on-treatment value (treatment endpoint = TEP)
- LOCF using last available value (study endpoint = SEP)

The *month x treatment endpoint* (of a certain variable, e.g., systolic blood pressure) is defined as the last available non-missing *on-treatment* observation (7-day rule) in the study period Day 1 to Day  $z$ , where  $z$  is the last day of the Month  $x$  visit window (for the  $x$  Month analysis). For example,  $z = 195$  is the last day of the Month 6 visit window. Therefore the *Month 6 treatment endpoint* for systolic blood pressure in a patient discontinuing study medication on Day 179 and reporting systolic blood pressures of 155, 190 and 165 mmHg on study Days 149, 180, and 189, respectively, would be 190 mmHg. This imputation is denoted as “TEP” in the visit window column of summary statistics tables.

The *month x study endpoint* (of a certain variable, e.g., systolic blood pressure) is defined as the last available non-missing observation in the study period Day 1 to Day  $z$ , where  $z$  is the last day of the Month  $x$  visit window (for the  $x$  Month analysis). This imputation is denoted as “SEP” in the visit window column of summary statistics tables.

In contrast to the *Month x treatment endpoint*, the *Month x study endpoint* may be an assessment obtained a long time after premature discontinuation of study treatment.

The *month x treatment endpoint* and *month x study endpoint* will be defined for Month 12 and Month 24 and labeled as Month X TEP and Month X SEP (e.g. Month 12 TEP and Month 12 SEP) in the analysis outputs. For the 24-month analysis, only Month 24 TEP and Month 24 SEP will be presented.

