9.4.4 Supportive analyses

The following analyses will serve as supportive analyses for the primary endpoint of tBPAR or eGFR (MDRD4)<50 mL/min/1.73m² at Month 12.

The analysis outlined for the primary endpoint in Section 9.4.2 will be repeated using compliant subjects in the FAS population.

Analysis on Per-Protocol Set

The analysis outlined for the primary endpoint in Section 9.4.2 will be repeated using the Per-Protocol Set.

Subgroup analysis

Subgroup analyses will be done for the primary composite endpoint of tBPAR or eGFR (MDRD4)<50 mL/min/1.73m² at 12 months for the subgroups defined by:

- recipient characteristics (recipient age group: <60 vs ≥60 yr, gender, race, region)
- donor/transplant characteristics (donor age group: <60 vs ≥60 yr, gender, cold ischemia time: < 20 vs ≥20 hr, end stage disease leading to transplant, donor type; living donor, standard criteria deceased donor and expanded criteria deceased donor; HLA mismatches: <=3 vs >3)
- CNI (tacrolimus vs. cyclosporine)
- Induction (basiliximab vs. rATG)
- Immunological risk (high vs. low)

Subgroup analyses will use the Z-test on event rates (proportions) and also present confidence intervals for the pairwise differences in proportions.

Risk factor analysis using a logistic regression model

To investigate prognostic variables that might have an impact on the primary efficacy endpoint, a logistic regression analysis will be performed to identify potential risk factors. For this analysis, the same variables to define the above subgroups as well as the interaction between treatment and CNI and the interaction between treatment and region will be used. In the model, recipient and donor age, cold ischemia time, and potentially HLA mismatches will be treated as continuous variables.

Analyses with other imputations for missing eGFR (MDRD4) at Month 12

In addition to the imputation method described in Section 9.4.3, the following imputation method will be used to impute missing 12-month eGFR value to define the primary variable – composite endpoint of tBPAR or eGFR (MDRD4) < 50 mL/min/1.73m². With these imputations, non-inferiority and superiority analyses described in Section 9.4.2 will be repeated.

- Subjects who lost their grafts will be assigned a value of zero for their 12-month eGFR;
- Otherwise, subject who had missing value including those who died with a functioning graft will have a 12-month eGFR imputed using the following imputation methods:

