For the composite efficacy failure (tBPAR, graft loss or death) at Month 24 and the composite endpoint of BPAR, graft loss or death at Month 12 and Month 24, Kaplan-Meier event rates will be estimated and compared between the everolimus plus reduced CNI and the MPA plus standard CNI arm. Similarly Kaplan-Meier event rates will be estimated and compared for AR, tAR, BPAR, tBPAR, humoral rejection, graft loss, death and the composite endpoint of graft loss or death. To assess time-to-event occurrence of efficacy endpoints, Kaplan-Meier plots will be produced and the log-rank test will be performed. A forest plot of KM event rate differences for efficacy endpoints will be produced. Severity of tBPAR will be tabulated by treatment.

As a key component of the primary endpoint (tBPAR or eGFR (MDRD4) < 50 mL/min/1.73 m²), the endpoint of eGFR (MDRD4) < 50 mL/min/1.73m² will be summarized with raw incidence rates and compared. A Z-test based 95% confidence interval will be provided.

For eGFR(MDRD4) at Month 12 and Month 24, analysis of covariance (ANCOVA) will be performed with treatment (everolimus vs MPA), CNI (CsA vs TAC), interaction of treatment and CNI, region, interaction of treatment and region, induction, donor type (living donor, deceased standard criteria donor and deceased expanded criteria donor), recipient gender and donor gender as factors, and recipient age and BMI, donor age, cold ischemic time and eGFR(MDRD4) at Month 1 as covariates. The missing Month 12 or Month 24 values will be imputed using the same methods as described in Section 9.4.3 and Section 9.4.4 except LOCF approach for Month 24, for which a Month 24 eGFR value will be imputed using the last nonmissing observation carried forward (LOCF) from Month 6 onwards as subjects will be maintained in the same CNI target range since Month 6.

Renal function and change from Month 1 (Week 4) will be summarized by visit with descriptive statistics and graphically presented by visit.

The evolution of renal function (eGFR by MDRD4) will be evaluated via a mixed effect model with intercept and subject as random effects and using with the same covariates/factors as used for the ANCOVA model. Based on the mixed effect model, the treatment groups will be compared, and slope of renal function evolution for each treatment group will be assessed.

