### 2.7.3.2 eGFR by MDRD4

The eGFR by MDRD4 analyses will be based on FAS with multiple imputation used as the primary method for the handling of missing data. Renal function and change from Week 4 will be summarized by visit with descriptive statistics. A two-sided t-test will be performed to compare the two treatment groups at each visit. A plot of mean and 95% CI of eGFR (MDRD4) by visit will be provided. These will be repeated for on-treatment renal function analyses.

In addition, if different CNI effect is shown from the logistic regression, eGFR(MDRD4) and change in eGFR(MDRD4) from Week 4 by visit will be summarized for the subgroups of CNI (CsA and TAC).

The proportion of patients by eGFR(MDRD4) range (<30, 30-<45, 45-<60, ≥60 mL/min/1.73m^2) will be summarized by visit.

For eGFR(MDRD4) at Month 12 and Month 24, analysis of covariance (ANCOVA) will be performed with covariates/factors of treatment, CNI, region, interaction of treatment and CNI, interaction of treatment and region, donor type, HLA mismatch (≤3 vs >3), induction therapy, recipient gender, recipient age, donor age, DGF, and eGFR (MDRD4) at Month 1. In the model, recipient and donor age will be treated as continuous variables. The missing Month 12 or Month 24 values will be imputed using the primary multiple imputation method.

The evolution of renal function (eGFR by MDRD4) will be evaluated via a mixed effect model with intercept and study day as random effects and using covariates/factors treatment, study day, CNI, region, interaction of treatment and study day, interaction of treatment and CNI, interaction of treatment and region, donor type, HLA mismatch (≤3 vs >3), induction therapy, recipient gender, recipient age, donor age, DGF, and eGFR (MDRD4) at Month 1. In the model, study day, recipient and donor age, and eGFR (MDRD4) at Week 4 will be treated as continuous variables. Unstructured variance-covariance can be assumed, and the eGFR (MDRD4) data at Week 4 and onward will be used. The denominator degrees of freedom will be calculated using the Kenward-Roger method. No imputation will be applied for missing data. Based on the mixed effect model, the treatment groups will be compared, slope of renal function evolution for each treatment group will be assessed, and eGFR(MDRD4) value at Month 12/24 will be estimated.

See dummy SAS codes below.

```
proc mixed method=ml;
  class trt CNI region donor HLA induction gender_r DGF usubjid;
```

```

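### SAP 4.2.3 carries renal values forward without the graft-loss zero rule used elsewhere, so a lost graft can keep a functioning eGFR in the Month 12 or 24 study-endpoint row

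*SAP*

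**What the plan says.** SAP 4.2.3 covers "Summary statistics by visit window for laboratory (including renal) and vital sign variables using two different conventions" of LOCF. The treatment endpoint (TEP) is the last on-treatment value. The study endpoint (SEP) "is defined as the last available non-missing observation in the study period Day 1 to Day" z, where z closes the Month 12 or Month 24 window (Day 450 or Day 810 in SAP Table 4-1). The section adds: "For the 24-month analysis, only Month 24 TEP and Month 24 SEP will be presented". It contains no graft-loss rule and no cross-reference to one.

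Section 4.2.3 does not define renal. SAP 4.5, headed Renal Variables, consists of three eGFR formulas: MDRD4, Hoek (cystatin C) and CKD-EPI.

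Elsewhere the plan has an explicit rule for lost grafts. Protocol 9.4.4 introduces its alternative imputations, LOCF among them, with this condition: "Subjects who lost their grafts will be assigned a value of zero for their 12-month eGFR". Only the remaining patients go on to LOCF or another method. Protocol 9.4.3 has the same rule for the main imputation. SAP 4.2.1.1 and 4.2.1.2 keep it for missing eGFR at visits from graft loss onwards, both for the composite and for eGFR by itself. SAP 2.7.3.2 analyses eGFR (MDRD4) on the full analysis set with multiple imputation, and repeats the summaries on treatment.

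**The concern.** Protocol 5.5.9 lists graft loss as a reason for leaving the study, and protocol 6.4 has it recorded that way on the completion form. Such patients will often have no eGFR after the loss. The SEP definition then picks up their last value before it, and a kidney that has failed appears in the Month 12 or 24 row as still filtering.

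Renal function at Months 12 and 24 is a stated secondary objective (protocol 2.2). Any arm with more graft losses would look better in the SEP row than under the plan's own zero rule. The SEP row would also differ from the multiple-imputation summary of the same variable, and nothing in the table would tell the reader why.

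**Working it through.** **1. The section's own example.** SAP 4.2.3 takes a patient who stops drug on Day 179 with systolic pressures of 155, 190 and 165 mmHg on Days 149, 180 and 189, and gives a Month 6 TEP of 190. Taking the last reading up to the earlier of z and Day 179 plus the on-treatment lag returns 190, with z = 195 or 225 and a lag of 2 or 7 days. The SEP for this patient is 165. The selection rule is therefore understood as intended: SEP takes the last recorded value, whatever has happened to the graft.

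**2. The rules side by side.**

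| Place | Use | After graft loss |
|---|---|---|
| Protocol 9.4.3 | main imputation, Month 12 | zero |
| Protocol 9.4.4 | alternative imputations, including LOCF | zero first, then the method |
| SAP 4.2.1.1, 4.2.1.2 | composite, and eGFR by itself | zero for missing values |
| SAP 4.2.3 | TEP and SEP summary rows | nothing stated |

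The one place in the current SAP that still carries eGFR forward is the one without the rule.

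**3. Size.** The documents give neither a graft-loss rate nor an eGFR shortly before loss, so both inputs are assumptions:

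- g = share of an arm's SEP row that lost the graft and has no later value: 1%, 3% or 5%.
- L = mean last eGFR before loss: 25, range 15-35 mL/min/1.73m².

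Excess in an arm mean over the zero rule = g × (L − 0):

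| g | L = 15 | L = 25 | L = 35 |
|---|---|---|---|
| 1% | 0.15 | 0.25 | 0.35 |
| 3% | 0.45 | 0.75 | 1.05 |
| 5% | 0.75 | 1.25 | 1.75 |

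Widening L to 10-50 gives 0.01 × 10 = 0.1 up to 0.05 × 50 = 2.5.

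Shift in the between-arm difference, with the same L in both arms = (g₁ − g₂) × L:

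- equal rates: 0
- 1 point apart: 0.01 × 15 to 0.01 × 35 = 0.15 to 0.35
- 3 points apart: 0.03 × 15 to 0.03 × 35 = 0.45 to 1.05

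For scale, protocol 1.1 cites mean eGFR of 57.1 against 51.7 in its tacrolimus-minimisation study, a difference of 5.4.

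**The case against.** The strongest reply is that the gap may be empty. Renal is undefined in 4.2.3; protocol Appendix 1 and SAP 4.6.1 use a laboratory heading for renal function that covers urea (and, in the protocol, creatinine) but not eGFR, and eGFR has its own missing-data rules. On this view 4.2.3 is silent but overrides nothing. Part of this stands: the point is conditional on eGFR being given SEP rows, and it would be wrong to say that the SAP as a whole ignores graft loss. But 4.5 makes eGFR the natural reading, and a programmer following 4.2.3 literally finds no zero rule there.

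The second reply is that these rows are descriptive. That stands in full: SAP 4.2.3 names no test or model.

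A reader might go further in three ways that the documents do not support.

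- **Carrying from Day 1 contradicts the protocol.** Protocol 9.5.2 does set a floor, "for which a Month 24 eGFR value will be imputed using the last nonmissing observation carried forward (LOCF) from Month 6 onwards", but for missing values in the Month 24 ANCOVA. The SAP change history (10-Nov-2016) removes LOCF imputation, and 2.7.3.2 uses multiple imputation for that ANCOVA. The protocol's Month 12 LOCF has no earliest day. A limit on a dropped model imputation does not govern summary rows.
- **The rows will be tested.** SAP 2.7.3.2 says "A two-sided t-test will be performed to compare the two treatment groups at each visit", and Table 4-1 lists TEP and SEP as re-aligned visits 13 to 16. But that sentence belongs to a paragraph on multiply imputed eGFR, and 2.7.3.1 works without imputation. Testing these rows is an inference; it is not stated, though nothing rules it out.
- **Early drug stops fill SEP with first-weeks values.** Patients who stop the regimen stay in the study, with central laboratory tests at Months 6, 9, 12, 18 and 24 (protocol Table 6-1), so only early study leavers are exposed. TEP is an on-treatment value by design.

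**Conclusion.** The concern holds in a narrow form. If eGFR receives SEP rows, SAP 4.2.3 as written lets a lost graft carry a functioning eGFR to Month 12 or 24, contrary to the zero rule that the protocol places ahead of LOCF and that the SAP keeps in its other eGFR imputations.

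The effect is confined to summary rows for a secondary objective. No primary, key secondary, ANCOVA or slope result changes. Within an arm the mean is too high by the graft-loss share times the carried value. Between arms the shift is a few tenths of a mL/min/1.73m² per percentage point of imbalance, and vanishes when graft-loss rates and mean carried values are equal. These sizes rest on assumed graft-loss shares and pre-loss eGFR, and on few patients having a measured eGFR after loss.

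**What to change.** Preferred: take eGFR and creatinine out of SAP 4.2.3. Section 2.7.3.2 already handles missing eGFR (MDRD4) by multiple imputation with an on-treatment repeat, and 2.7.3.1 summarises the other two formulas on treatment without imputation.

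If the rows are kept, add to 4.2.3 that:

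- eGFR is zero from graft loss onwards in the SEP rows, in line with 4.2.1.1;
- TEP remains purely the last on-treatment value, since a zero there could bring in an off-treatment value against its definition;
- the between-arm t-tests in 2.7.3 are not applied to TEP or SEP rows.

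No Month 6 floor is needed.

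The cost is one to three sentences. The downside is that the renal LOCF rows disappear, or that SEP means become slightly lower. The same edit can settle two other mismatches in 4.2.3: Day 195 as the end of the Month 6 window against Day 225 in Table 4-1, and a seven-day on-treatment rule for laboratory and vital sign values against two days in SAP 2.1 and 2.1.1.5. Neither changes the worked example.

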#### 4.2.4 Imputation of Incomplete Dates

Although not the rule, partially or completely missing dates occur. Known dates with this issue are the start date on the Medical History eCRF page, start and end dates on the Concomitant Medications eCRF page or Surgical and Medical Procedures eCRF page, and occasionally, start and end dates on the Adverse Event eCRF.

Any date incompletely reported is split into its day, month, and year components. In SAS, a numeric date variable can only be defined if all three date components are known; incomplete dates are to be handled as text strings (character-type variables); as such, they could not be easily processed. An imputation rule for incomplete dates will be performed.

##### 4.2.4.1 Incomplete Start Date for Adverse Events and Concomitant Medication

This algorithm is expressed in the Variable Source Derivation column as #IMPUTA $EV(event)$  where *event* is the partial start date of the adverse event.

The following table explains the notation used in the logic matrix. Please note that **missing start dates** will not be imputed.

Note, if the imputed AE (or CM) start is after AE (or CM) end date, then set AE (or CM) start equal to AE (or CM) end date.

	Day	Month	Year
Partial Adverse Event (or Concomitant Medication) Start Date	Not used	MON	YYYY
Treatment Start Date (TRTSDT)	Not used	TRTM	TRTY

The following matrix explains the logic behind the imputation.

	MON MISSING	MON < TRTM	MON = TRTM	MON > TRTM
YYYY MISSING	NC	NC	NC	NC
YYYY < TRTY	(D)	(C)	(C)	(C)
YYYY = TRTY	(B)	(C)	(A)	(A)

YYYY > TRTY	(E)	(A)	(A)	(A)
----------------	-----	-----	-----	-----

The following table is the legend to the logic matrix.

Relationship	
Before Treatment Start	Partial date indicates AE (or CM) start date prior to Treatment Start Date
After Treatment Start	Partial date indicates AE (or CM) start date after Treatment Start Date
Uncertain	Partial date insufficient to determine relationship of AE (or CM) start date to Treatment Start Date
Imputation Calculation	
NC / Blank Uncertain	No convention
(A) After Treatment Start or Uncertain	MAX( 01MONYYYY, TRTSDT+1 )
(B) Uncertain	TRTSDT+1
(C) Before Treatment Start	15MONYYYY
(D) Before Treatment Start	01JULYYYY
(E) After Treatment Start	01JANYYYY

#### 4.2.4.2 Incomplete End Date for Adverse Events

Missing AE end dates will not be imputed.

#### 4.2.4.3 Incomplete End Date for Concomitant Medication

The following table explains the notation used in the logic matrix. Please note that **missing end dates** will not be imputed.

	Day	Month	Year
Partial Conmed. end Date	Not used	MON	YYYY
Last Contact Date (LASTDT)	Not used	LSTM	LSTY

MON MISSING	MON < LSTM	MON = LSTM	MON > LSTM
-------------	------------	------------	------------

YYYY MISSING	NC	NC	NC	NC
YYYY < LSTY	(C)	(A)	(A)	(A)
YYYY = LSTY	(B)	(A)	(B)	(A)
YYYY > LSTY	(C)	(A)	(A)	(A)

Relationship	
Before Last contact date	Partial date indicates CM end date prior to Last Contact Date
After Last contact date	Partial date indicates CM end date after Last Contact Date
Uncertain	Partial date insufficient to determine relationship of CM end date to Last Contact Date
Imputation Calculation	
NC / Blank Uncertain	No convention
(A) Before/After Last contact date	Last day MONYYYY
(B) Uncertain	LASTDT
(C) Before/After Last contact date	31DECYYYY

At the Month-12 analysis, if the above logic is applied and the imputed end date is after the month 12 cut-off date, then the imputed end date is replaced with the month 12 cut-off date.

#### 4.2.4.4 Medical History

Start dates on the Medical History eCRF page are rather frequently incomplete. No dates will be imputed. Incomplete dates (if any) will be listed.

### 4.3 Definition/Derivation of Efficacy Variables

All efficacy endpoints regarding biopsy described below will be identified from local pathologists' evaluation of all biopsy readings. All acute rejections are recorded in the clinical database on the Kidney allograft rejection and Kidney allograft biopsy eCRFs.

#### 4.3.1 Antibody-Mediated (Humoral) Rejection (AMR)

A rejection is considered as an AMR if:

- Acute antibody mediated rejection = "Yes" from kidney allograft biopsy eCRF page

Date of rejection will be “date rejection was first suspected” on the Kidney allograft rejection eCRF, or if missing, the first available date of the biopsy of the particular rejection episode on the Kidney allograft biopsy eCRF page.

#### 4.3.2 Acute Rejection (AR)

A rejection is considered an AR if:

- Primary clinical diagnosis = “Acute rejection” or “Acute and chronic rejection” from Kidney allograft rejection eCRF page; **OR**
- Antibody-mediated rejection (see above); **OR**
- Acute T-Cell mediated rejection = “Yes” from Kidney allograft biopsy eCRF page.

Date of AR will be “date rejection was first suspected” on the Kidney allograft rejection eCRF, or if missing, the first available date of the biopsy of the particular rejection episode on the Kidney allograft biopsy eCRF page.

#### 4.3.3 Treated Acute Rejection (tAR)

A rejection is considered a tAR if:

- Acute rejection (see above); **AND**
- Was anti-rejection therapy administered? = “yes” from Kidney allograft rejection eCRF

Date of tAR will be the date of the corresponding AR (note: tAR is a subset of AR).

